6.3. Concomitant Therapy

6.3.1. Diabetes Management and Insulin Use

All participants should receive intensive diabetes management of their T1D using approved therapies according to the recommendations of ADA to achieve glucose levels that appear to decrease some of the short-term and long-term sequelae of T1D. Currently the glycemic targets by the ADA are focused at management strategies to achieve an HbA1c level of <7.5% (58 mmol/mol) for individuals 17 years old and younger and <7.0% (53 mmol/mol) for those 18 years and older, while minimizing severe or frequent hypoglycemic events. If there are local, regional, or national recommendations to be followed that supersede ADA recommendations, these glycemic control targets (ie, HbA1c or glucose levels) should not be more liberal (ie, higher) than the ADA recommendations. The Investigator will document, in the case report form (CRF) and/or the source documents, the glycemic goals and the guidelines being followed.

The glycemic goal should be attempted through proper glycemic monitoring, administration of exogenous insulin, and monitoring of activity level and diet. Exogenous insulin may include rapid, intermediate, and/or long-acting insulins, administered intermittently or via the use of a personal insulin pump. Blood glucose levels should be measured at least 4 times a day, including before meals and before bedtime. Approaches to achieve these HbA1c goals will be the responsibility of the participant, their caregivers, and their healthcare providers.

Insulin use, including the type of products, dosages, and dosing schedules, is expected to change during the course of the study. As part of routine T1D clinical care, if the caring physician judges it to be clinically appropriate, a participant's insulin dose may be increased, reduced, or even discontinued.

Insulin Discontinuation

If a participant has achieved a HbA1c level of $\leq 6.5\%$ with insulin use of ≤ 0.25 U/kg/day, insulin therapy can be discontinued. The participant's blood glucose and HbA1c levels should continue to be monitored per protocol, and urine ketones should be tested at home once a day. During routine blood glucose monitoring, if the participant's blood glucose level exceeds 200 mg/dL and/or urine ketone level is moderate or greater, the participant should consult with their primary physician and/or the clinical site staff for further evaluation. If the fasting blood glucose exceeds 126 mg/dL or HbA1c exceeds 6.5%, as documented by repeat testing, the resumption of insulin therapy should be considered.

6.3.2. Prophylactic Medications

Ibuprofen and antihistamine will be administered prophylactically prior to teplizumab infusion on the first 5 days of treatment. After Day 5, the use of pre-medication is optional. If ibuprofen is contraindicated, acetaminophen should be given instead. Further dosing of ibuprofen, antihistamines, and/or acetaminophen can be used as needed for fever, malaise, headache, arthralgia, or rash. All prophylactic medications administered should be recorded on the concomitant medication CRF.

6.3.3. Prohibited Medications

Participants will be instructed not to use steroids, (eg, prednisone [topical or systemic]), other immunosuppressive agents, or chronic inhaled or nasal corticosteroids during this trial in order to reduce infectious risks and to prevent possible impact on diabetes outcome. A short course (ie, approximately 2 weeks or less) of systemic (including oral, inhaled or parenteral) corticosteroids may be used for treatment of a transient condition. In the event of a medical condition requiring glucocorticoid treatment, they may be used after discussion with the Medical Monitor. However, no individual will be withdrawn from analysis if this occurs.

Participants will be instructed not to receive live vaccinations for 1 year after dosing. In addition, participants should not receive vaccination with a killed virus vaccine within 8 weeks after the last dose of the study drug, unless this is approved by the Medical Monitor.

6.3.4. Emergency Precautions

Before every infusion of study drug, appropriate emergency equipment and trained personnel should be present. At a minimum, the following will be available:

- Epinephrine 1 mg doses (or resuscitation dose recommended by local, regional or national authorities) for IV injection
- Dexamethasone 10 mg (or equivalent glucocorticoid) for IV injection
- Diphenhydramine: 50 mg (or equivalent antihistamine) for IV injection
- Resuscitation equipment and other supplies for the emergency management of an allergic/toxic reaction.

If AEs develop during infusion, the infusion may be slowed or interrupted, as determined by the Investigator. If interrupted, the infusion may be restarted, preferably at a slower rate, if deemed reasonable by the Investigator. Any changes in the infusion rate must be recorded with the reason for the change. In any cases of AEs determined or suspected to be related to the infusion of the study drug, the participant should be treated using appropriate medical practices and procedures.

During or after the infusion of study drug, if a participant experiences any of the following signs, the participant will be observed, and the severity of the reaction will be evaluated:

- Fever of $>38.5^{\circ}\text{C}$ (101.3°F)
- Rigors or myalgias
- Pain, swelling, or edema near the infusion site
- Local or systemic rash
- Mucosal congestion or edema
- Significant (eg, 30%) drop in systolic or diastolic blood pressure or increase in resting heart rate
- Hyperventilation, wheezing or difficulty breathing

- Change in mental status

Acetaminophen (or similar drug) and/or additional NSAID may be given if needed, glucocorticoid treatment may be considered. The participant should be treated using appropriate medical practices and procedures. The participant will be continuously monitored until their clinical status returns to baseline or is significantly improved.

If an infusion is discontinued, an estimate on the volume of the infusion given and a quantitative assessment of the remaining volume should be documented.

The Medical Monitor should be notified of all cases of actual or suspected infusion reactions and AEs thought to be related to the study drug infusion.

7. Interruption or Discontinuation of Study Drug Treatment and Participant Discontinuation/Withdrawal

A participant will not be automatically withdrawn from the study if they temporarily or permanently discontinue study drug before the end of the treatment course. If a participant permanently discontinues study drug for any reason, they should be encouraged to return for the Early Termination visit.

Unless lost to follow-up, SAEs must be reported for participants who withdraw early from the study for one year after their last study drug dose (Section 8.4.1).

7.1. Interruption of Study Drug Treatment

Blood samples will be drawn for clinical laboratory tests, as listed in Section 1.3, and the results will be reviewed by the Investigator before the study drug can be administered on each day of the treatment.

Study drug dosing may be interrupted temporarily, for an individual participant, if any of the following medically important events occur:

- A significant infection, defined as:
 - Any severe infection meeting SAE criteria (Section 10.3.2), or
 - Any clinically significant infection not meeting SAE criteria but per Investigator's judgment might put the participant at risk, or
- An SAE, a study drug-related severe AE, or an AE that puts a participant at risk, defined as:
 - Any SAE or
 - Any severe AE that is considered related (possibly, probably, or very likely related) to study drug (as defined in Section 10.3.1), including but not limited to an infusion reaction categorized as a severe or SAE by the Investigator.
 - Any AE (including mild or moderate) of any relatedness to study drug that leads to the Investigator to believe that further dosing of study drug during that course puts the participant at undue risk.
- If any of the following out-of-range lab results is observed (normal range per local lab reference ranges), the test may be repeated on the same day. If the repeated test result normalizes, that day's dose may be given. If the value is still in the indicated range or worsens, or if the test cannot be repeated on the same day, that day's dose should be withheld.
 - ALT and/or AST >3 x ULN but ≤ 5 x ULN
 - Total bilirubin >2 x ULN but ≤ 3 x ULN
 - Platelet count $>50,000$ but $\leq 100,000$
 - Hemoglobin >8.5 g/dL but ≤ 10 g/dL

Note: When clinical and laboratory abnormalities are considered related to T1D disease activity (ie, hypoglycemia and hyperglycemia) and study drug is not considered a contributing factor, administration may not need to be modified. The site Investigator should consult with the Sponsor if this is encountered.

If the above events resolve within 2 days, study drug dosing may be resumed according to the original schedule. The treatment course will not be extended beyond 12 days.

If the above events do not resolve after 2 consecutive days of interruption, the Medical Monitor must be consulted regarding continuation of study drug dosing.

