7.2. Discontinuation of Study Drug Treatment

The study drug should be discontinued permanently if any of the following events occur:

- The Investigator believes that for safety or tolerability reasons it is in the best interest of the participant to discontinue study drug.
- A female participant becomes pregnant. Note: The “Pregnancy Report Form” should be submitted for all pregnancies that occur in a study participant. Pregnancy should be followed for outcome and any premature terminations reported. The health status of the mother and child including date of delivery and the child’s sex and weight should be reported after delivery.
- A severe infection requiring inpatient hospitalization or repeated doses of parenteral antibiotics
- A severe hypersensitivity reaction, such as anaphylaxis or angioedema with or without requiring hemodynamic support (ie, epinephrine and/or blood pressure medications) or mechanical ventilation, to the study drug or an infusion reaction (including cytokine release syndrome) with signs or symptoms categorized as an SAE.
- The participant has a clinically significant cardiovascular event.
- The participant is diagnosed with a malignancy, lymphoma or a lymphoproliferative disorder.
- If any of the following lab values is observed (normal range per local lab standard), the next study drug dose should be held until a repeat test is obtained and evaluated. If the out-of-range result is confirmed on two consecutive dosing days, the participant should be discontinued from any further study drug treatment.
 - ALT and/or AST >5X ULN
 - Total Bilirubin >3X ULN
 - ALT and/or AST >3X ULN **AND** Total Bilirubin >2X ULN (Hy’s Law criteria)
 - Platelet count <50,000/ μ L
 - Neutrophil count <500 cells/ μ L
 - Hemoglobin of <8.5 g/dL

- Any \geq Grade 3 AE during dosing other than:
 - Lymphopenia
 - Neutropenia
 - Low total WBC
 - Hypoglycemia or symptoms and signs of a hypoglycemic episode
 - Hyperglycemia or symptoms and signs related to hyperglycemia
 - Fatigue or malaise
 - Insomnia
 - Cheilitis
 - Dry skin
 - Nail changes
 - Hot flushes or flashes
 - Headache
 - Myalgia
 - Flu-like syndrome
- Any medically important event such as a concurrent illness, complications, or abnormal laboratory result that, in the opinion of the Investigator, contraindicates continued dosing of the participant

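### Protocol Section 7.1 permits re-dosing after events that Section 7.2 makes permanent stops, and neither section says which governs

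*Protocol*

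**What the plan says.** Protocol Section 7.1 lists three kinds of trigger for temporary interruption: significant infections, including severe ones that are SAEs; any SAE, any related severe AE, or any AE that the Investigator thinks makes further dosing unduly risky; and four laboratory ranges. The related severe AEs come with one named example: "including but not limited to an infusion reaction categorized as a severe or SAE by the Investigator".

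Two rules then apply to the whole list. The first is "If the above events resolve within 2 days, study drug dosing may be resumed according to the original schedule". The second is "If the above events do not resolve after 2 consecutive days of interruption, the Medical Monitor must be consulted regarding continuation". Neither sets any listed event apart.

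Protocol Section 7.2 opens with "The study drug should be discontinued permanently if any of the following events occur". Its list includes "an infusion reaction (including cytokine release syndrome) with signs or symptoms categorized as an SAE"; "A severe infection requiring inpatient hospitalization or repeated doses of parenteral antibiotics"; severe hypersensitivity; clinically significant cardiovascular events; malignancy; and any ≥ "Grade 3 AE during dosing other than" 14 exempt types. For its listed laboratory values it has a separate procedure: hold the next dose, repeat the test, and stop if the result is confirmed on two consecutive dosing days.

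Section 7.1 does not mention Section 7.2, nor the reverse. The introduction to Section 7 and Section 6.3.4 (Emergency Precautions) do not rank them. The SAP sets no dosing rules.

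**The concern.** Some clinical events sit in both lists with different consequences. The single-parameter liver, platelet and haemoglobin limits are tiered: a milder range leads to a hold in Section 7.1 and a worse one to the stopping procedure in Section 7.2. The clinical events have no such tiering. The only clinical event that Section 7.1 gives as an example is one that Section 7.2 generally treats as a permanent stop.

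At stake is participant safety, which is the primary objective. A site that consulted Section 7.1 alone could re-dose a participant whose SAE-level cytokine release settled within a day. Clear stopping rules matter here because some participants are being re-exposed after an interval longer than any tested before, with the effect of anti-drug antibodies unknown (Protocol Section 4.2). The same section reports no increase in adverse events with second courses, so this is an argument for clarity and not evidence of excess risk.

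**Working it through.** No rate, power or sample size is involved. The check is to match each Section 7.1 trigger against each Section 7.2 stop, using the protocol's own definitions, and then to look for any sentence that ranks the two.

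Two definitions link the lists. Section 10.3.4 equates Grade 3 with severe. Section 10.3.2 makes inpatient hospitalisation a criterion for an SAE and gives invasive or malignant cancers as examples of important medical events usually considered serious.

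| Event during dosing | How it enters Section 7.1 | Section 7.2 |
|---|---|---|
| Infusion reaction or cytokine release syndrome that is an SAE | Named example | Named permanent stop |
| Severe infection with inpatient admission | Severe infection that is an SAE, through Section 10.3.2 | Named permanent stop |
| Non-exempt Grade 3 or higher AE, related to drug | Related severe AE, through Section 10.3.4 | Permanent stop, whatever the relatedness |
| Non-exempt Grade 3 or higher AE, serious | Any SAE | Permanent stop |
| Severe hypersensitivity that is serious | Any SAE | Named permanent stop |
| Clinically significant cardiovascular event that is serious | Any SAE | Named permanent stop |
| Malignancy | Any SAE | Named permanent stop |
| ALT/AST >3 to 5 x ULN together with bilirubin >2 to 3 x ULN | Both values lie in the hold ranges | Hy's Law line: stop if confirmed on two consecutive dosing days |

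Three details follow.

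1. A severe infusion reaction that is not an SAE is still Grade 3. Section 7.2 therefore stops the drug unless the event is recorded under an exempt term such as headache, myalgia or flu-like syndrome.
2. For the Hy's Law combination, suppose the values are raised on one dosing day, confirmed on the next, and back to normal on the day after. Section 7.1 would let dosing resume, because the event resolved within 2 days. Section 7.2 would already have required a permanent stop.
3. For events that cannot resolve in 2 days, such as malignancy, the difference lies in the second rule of Section 7.1. It leaves continuation open for discussion with the Medical Monitor, whereas Section 7.2 closes it.

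Triggers that meet no Section 7.2 criterion do not conflict. Examples are a mild or moderate AE, a severe AE of an exempt type that is not otherwise a stop, and a single laboratory value in a Section 7.1 range. No sentence giving either section precedence was found in the protocol or the SAP.

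**The case against.** The strongest reply is that the two sections do not give opposing orders. Section 7.1 says that dosing may be interrupted and may be resumed; Section 7.2 says that it should stop. A permission does not cancel an instruction, so a site that always applies Section 7.2 complies with both. Section 7.2 follows directly, and the tiered laboratory limits show the intended structure: a broad net first, then a stricter subset. This stands. A reader might infer that the protocol directs sites to re-dose after these events, or that no site could satisfy both sections. The text supports neither reading.

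The second reply is that other safeguards exist. SAEs go to the sponsor immediately, and within 24 hours at most (Section 8.4.1.1). AESIs follow the same requirement (Section 10.3.4), and in the protocol they include all infections and Grade 3 or higher cytokine release, allergic reaction and rash (Section 10.3.3). The Medical Monitor is to be told of infusion reactions and also of AEs thought to be related to the infusion (Section 6.3.4), which may cover much of the drug-related overlap. The Investigator may stop the drug on judgement at any time (Section 7.2). These lower the risk. They are notices and discretionary powers, though: none says which section governs or requires a reply before the next dose. The 24-hour Medical Monitor notice in Section 7.2 applies only once the drug has been permanently discontinued. Section 7.1 requires consultation only for events still unresolved after 2 consecutive days.

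**Conclusion.** The point holds as a gap in the dosing rules. Section 7.1 applied alone permits re-dosing that Section 7.2 rules out, and nothing in the documents ranks the two. It is worth correcting on safety grounds, although a careful reader would probably let Section 7.2 govern.

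Its size cannot be given as a number. A reader might turn to the TN-10 grade table in Protocol Section 2.3. That table covers a 14-day course in Stage 2 participants and does not separate exempt, laboratory or post-dosing events, so it does not show how often the overlap would occur. A reader might also try to calculate by how many hours a safety report could trail the next infusion. Section 8.4.1.1 does not say when its 24-hour limit starts, so that calculation would rest on an assumption about the clock.

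The effect on analysis is small. The study is single-arm and descriptive, with at most 30 participants under the SAP (SAP Section 6). Interruptions and AEs leading to discontinuation are listed case by case (SAP Sections 7.6 and 7.7.1). Which section a site followed could move a participant into or out of the discontinuation counts, but the listings would show it.

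The conclusion rests on the protocol's own equation of severe with Grade 3 and on its SAE criteria. It needs no outside figure.

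**What to change.** Add one sentence to Protocol Section 7.1, after the list of events:

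> Interruption and resumption under this section apply only to events that meet no criterion in Section 7.2; where an event meets both, Section 7.2 governs (for the laboratory values listed in 7.2, including the Hy's Law combination, its hold/repeat/confirm rule applies).

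Nothing needs to be removed from the Section 7.1 list. The wording covers every row of the table, including events that reach Section 7.1 only as SAEs. The cost is one sentence in an amendment, with no extra data, visits or staff.

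The documents do not say whether dosing has finished. If it has, the exposure listing already planned in SAP Section 7.6 can be read against the AE listings to see whether anyone was re-dosed after an event that met a Section 7.2 criterion.

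### Protocol Sections 7.1 and 7.2 overlap with no stated precedence: some events that 7.2 makes stop events may, under 7.1, be followed by resumed dosing

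*Protocol*

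**What the plan says.** Protocol Section 7.1 (interruption) lists events for which dosing may be held: significant infections, any SAE, drug-related severe AEs, other AEs that the investigator thinks make further dosing too risky, and four bands of laboratory values. The related-severe item reads "Any severe AE that is considered related (possibly, probably, or very likely related) to study drug" and carries the example "including but not limited to an infusion reaction categorized as a severe or SAE by the Investigator". The section then gives two outcomes for everything listed. The first is "If the above events resolve within 2 days, study drug dosing may be resumed according to the original schedule". The second is "If the above events do not resolve after 2 consecutive days of interruption, the Medical Monitor must be consulted", the subject of that consultation being whether dosing continues.

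Protocol Section 7.2 opens with "The study drug should be discontinued permanently if any of the following events occur". Its list includes "A severe infection requiring inpatient hospitalization or repeated doses of parenteral antibiotics", "an infusion reaction (including cytokine release syndrome) with signs or symptoms categorized as an SAE", a diagnosis of malignancy, any AE of Grade 3 or higher during dosing apart from 14 exempt terms, and laboratory criteria that end treatment once confirmed on two consecutive dosing days.

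Neither section refers to the other. No rule of precedence appears elsewhere in the protocol, and the SAP does not take up the question.

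**The concern.** A site facing an event on both lists finds one section that lets it resume and another that tells it to stop. Section 7.1 requires Medical Monitor consultation only when the event has lasted beyond two consecutive days of interruption. Taken alone, it therefore permits re-dosing after a 7.2 stop event that clears sooner, with nobody outside the site having agreed. Protocol Section 6.3.4, which lets the investigator restart an interrupted infusion, points the same way.

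The main stake is participant safety on the next dose. A secondary stake is consistency of reporting in a study whose primary objective is safety. The SAP tabulates early discontinuation of study drug by reason and lists protocol deviations (SAP Section 7.3), and summarises TEAEs leading to treatment discontinuation (SAP Section 7.7.1). If sites follow different sections, the same event can be counted differently, and it is open to argument whether a resumption is a deviation.

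**Working it through.** The plan gives no figure to reproduce, so the check matches each 7.1 trigger against the 7.2 triggers, using the protocol's own SAE definition (Section 10.3.2) and severity scale (Section 10.3.4).

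| Event | Route into 7.1 | Route into 7.2 | What links them |
|---|---|---|---|
| Infusion reaction categorised as an SAE | Named in the related-severe example; also an SAE of any kind | Named: "an infusion reaction (including cytokine release syndrome) with signs or symptoms categorized as an SAE" | Direct; no definition needed |
| Severe infection that is an SAE through hospitalisation | Severe infection satisfying the SAE definition | Named: "A severe infection requiring inpatient hospitalization or repeated doses of parenteral antibiotics" | Inpatient hospitalisation is SAE criterion (c) in 10.3.2 |
| Drug-related AE of Grade 3 or higher during dosing, outside the exempt terms | Severe AE considered related | The Grade 3 or higher item | 10.3.4 equates Grade 3 with severe |
| ALT/AST above 3x ULN with bilirubin above 2x ULN | Falls in the hold bands (ALT/AST above 3x to 5x; bilirubin above 2x to 3x) | Hy's Law item, once confirmed on two consecutive dosing days | Same laboratory values |
| Other SAEs that are stop events, such as malignancy | SAE of any kind | Malignancy item | 10.3.2 gives cancers as an SAE example |

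**Exempt terms.** The 7.2 list has 14: lymphopenia, neutropenia, low total WBC, hypoglycaemia, hyperglycaemia, fatigue or malaise, insomnia, cheilitis, dry skin, nail changes, hot flushes, headache, myalgia and flu-like syndrome. Infusion reaction is not among them. So 7.1's own example of a severe but non-serious infusion reaction is, at Grade 3 during dosing, a 7.2 stop event.

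**The overlap is partial.** Section 7.1 keeps its own ground, for example related severe AEs within the exempt terms and serious infections that do not meet the 7.2 infection criterion.

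**Which overlaps matter in practice.** Resumption without consultation needs the event to clear within two days. That is plausible for a short-lived infusion reaction, less so for a hospitalised infection, and not realistic for malignancy. Where the event persists, as with continuing Hy's Law values, 7.1 sends the question of continuation to the Medical Monitor, while 7.2 has already answered it.

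**Whether other provisions close the gap.**
- SAEs go to the sponsor within 24 hours (8.4.1.1).
- AESIs follow the SAE reporting rules (10.3.4). The protocol's AESI list (10.3.3) includes all infections and Grade 3 or higher cytokine release syndrome, hypersensitivity, rash, liver abnormality and thrombocytopenia.
- The Medical Monitor should be told of infusion reactions and infusion-related AEs (6.3.4).
- The 24-hour Medical Monitor notice in 7.2 starts only once a participant has been permanently discontinued, so a site following 7.1 never triggers it.

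All four are notifications. None requires agreement before the next dose, and with daily infusions a report made within 24 hours need not arrive before that dose.

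**The case against.** The strongest reply is that the two sections form a ladder. Section 7.1 is permissive at both ends: dosing may be held and may be resumed. Section 7.2 is directive and makes no exception for quick resolution. A broad list for holding a dose and a narrower list for stopping read naturally as hold, evaluate, and stop if 7.2 is met. Read together, resuming after a 7.2 event breaches 7.2. The window for error is also narrow: the event must meet 7.2, clear within two days, and be handled by an investigator who overlooks 7.2. Reporting is wide, since many severe non-serious events are AESIs and are reported like SAEs. No endpoint definition turns on the point, and SAP Section 7.2 plans no inferential analysis.

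Most of this stands. A reader might infer that the sections contradict each other so that a site cannot comply with both. The documents do not support that, because stopping complies with both. What the reply does not remove is that the protocol never states the ladder, that 7.1 offers resumption for an event it names and 7.2 also names, and that the safeguards inform others without requiring their prior agreement.

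A reader might also give heavy weight to re-exposure, since for prior teplizumab recipients this is a second course after an interval longer than has been tested. Protocol Section 4.2 says that too, but it also reports no safety concern and no excess of adverse events with second courses. Re-exposure adds only modest weight.

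**Conclusion.** The point holds as an unstated precedence between two overlapping dosing rules. One overlap is explicit (the SAE infusion reaction); the others follow from the protocol's own definitions. The five rows above are the overlaps identified and are not offered as a closed count, because 7.1's coverage of any SAE can meet other 7.2 items. The practical risk is small and is mainly re-dosing after a short-lived severe or serious infusion reaction without prior Medical Monitor agreement. It is still worth fixing, because it concerns a dosing-safety rule and costs almost nothing.

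The number affected cannot be derived. A reader might infer one from the TN-10 figures in Protocol Section 2.3: 20 of 44 teplizumab participants (45.5%) had a related Grade 3 event and 15 (34.1%) had exempt lymphopenia, so 20 - 15 = 5, and 5/44 x 30 = 3.4 of the 30-participant maximum, with a ceiling of 20/44 x 30 = 13.6. The documents do not support that use:
- The 7.2 item applies only during dosing. Table 1 gives no dosing window, and TN-10 had a median follow-up of 745 days.
- The subtraction treats the 15 as distinct participants among the 20 and removes only lymphopenia, although neutropenia and low WBC are also exempt.
- The ceiling needs every participant with Grade 3 lymphopenia to have had a second, non-exempt Grade 3 event.
- SAP Section 7.10 describes enrolment as small, so 30 is not a realistic base.
- Above all, the figures count possible stop events, not wrongful resumptions.

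The cytokine release figure (0.06 x 30 = 1.8) fails similarly: it covers all grades, and Section 2.3 describes most cases as mild to moderate.

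**What to change.** Add one sentence to Protocol Section 7.1: *This section, including resumption of dosing, applies only when no Section 7.2 criterion is met; otherwise Section 7.2 governs.* Then remove the infusion-reaction example from 7.1, or qualify it with a pointer to 7.2 for reactions that are SAEs or Grade 3 or higher.

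The sentence settles every overlap in the table, including the Hy's Law values, for which 7.2's hold, repeat and confirm steps then apply. It does not hand all 14 exempt terms to 7.1 without limit. Section 7.1 covers drug-related severe AEs in those terms only where no other 7.2 criterion is met; neutropenia, for example, is exempt as a term, but a confirmed neutrophil count below 500/µL still stops treatment.

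The cost is one sentence, one edited example and a clarification to sites. There is no new visit or procedure, and no loss of treatment beyond what 7.2 already directs.
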